8.8.4 Analysis of Suicidal Ideation and Behavior

Suicidal ideation and behavior will be summarized according to suggestions made in the C-SSRS Scoring and Data Analysis Guide [6]. A positive response for suicidal ideation is counted when a participant answers “yes” to any one of the five suicidal ideation questions (Categories 1-5) on the C-SSRS (i.e., a score >0 for suicidal ideation). Serious suicidal ideation is a suicidal ideation score of 4 or 5. A positive response for suicidal behavior occurs when a participant answers “yes” to any one of the five suicidal behavior questions (Categories 6-10) on the C-SSRS (i.e., a score >0 for suicidal behavior). The number and percent of positive responses of Positive Ideation, Serious Ideation, and Positive Behavior will be tabulated by treatment group and time period (lifetime, screening, baseline, each Experimental Session (pre- and post-IP), Integrative Sessions, and endpoints). Frequency and incidence of positive or serious ideation and suicidal behavior will be presented using descriptive statistics in tabular format.

8.8.5 Analysis of Vital Signs

Vital signs (heart rate, BP, and body temperature) for Experimental Sessions will be summarized using descriptive statistics in tabular format listing values at pre-IP, prior to the supplemental dose, and at the end of each Experimental Session by treatment group. Change from Baseline in vital signs will be compared by treatment group with appropriate statistical techniques.

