	Treatment 1					Treatment 2					Treatment 3				Primary Outcome	Study Termination
Visit	V5	V6	V7	V8	V9	V10	V11	V12	V13	V14	V15	V16	V17	V18	V19	V20
Visit Description	Exp. 1	Int. 1.1	Int. 1.2 ^G	CAPS-5 T2: Tele-medicine	Int. 1.3 ^G	Exp. 2	Int. 2.1	Int. 2.2 ^G	CAPS-5 T3: Tele-medicine	Int. 2.3 ^G	Exp. 3	Int. 3.1	Int. 3.2 ^G	Int. 3.3 ^G	CAPS-5 T4 Outcome: Tele-medicine ^F	Study Termination
Visit Timing	4 to 7 days after V3; 1 to 4 days after V4	Morning after V5	3 to 14 days after V5	18 to 30 days after V5	20 to 34 days after V5; 1 to 7 days before V10	21 to 25 days after V5	Morning after V10	3 to 14 days after V10	18 to 30 days after V10; 1 to 7 days before V15	20 to 34 days after V10; 1 to 7 days before V15	21 to 35 days after V10	Morning after V15	3 to 14 days after V15	21 to 35 days after V15	105 to 147 days after V3; 42 to 70 days after V15	105 to 147 days after V3; 1 to 9 days after V19
Past/Current Medication & Adherence	✓	✓	✓		✓	✓	✓	✓		✓	✓	✓	✓	✓		✓
Drug Screen	✓					✓					✓					
Pregnancy Screen	✓					✓					✓					
Record	✓	✓	✓	✓	✓	✓	✓	✓	✓	✓	✓	✓	✓	✓	✓	✓
All AEs ^A	✓	✓	✓		✓	✓	✓	✓		✓	✓	✓	✓	✓		✓
Randomization ^B	✓															
Container Assignment ^B	✓					✓					✓					
Administer IMP	✓					✓					✓					
8-hour Exp. Session	✓					✓					✓					
BP, Pulse, Temperature ^C	✓					✓					✓					✓ ^D
Overnight Stay	✓					✓					✓					
90-minute Integrative Session		✓	✓		✓		✓	✓		✓		✓	✓	✓		
Phone Call Follow-up ^E		✓					✓					✓				
Weight																✓

^A All Adverse Events (AEs) includes collecting Serious Adverse Events, AEs of Special Interest, AEs of Psychiatric Status, AEs requiring medical advice or attention, AEs that indicate withdrawal of a participant, and all other AEs

^B Randomize 24 to 48 hours prior to first Experimental Session; obtain container assignment 24 to 48 hours prior to each Experimental Session

^C During Experimental Sessions, vitals are measured before Investigational Product administration, immediately before the supplemental dose is administered (or would be, if supplemental dose not given), and approximately 8 hours after initial dose, and as needed

^D At Study Termination, only blood pressure needs to be measured

^E 14 days of phone call follow-up: Days 2, 4, 6, 7, 8, 10, 12, 14 after each Experimental Session

^F All visits must be scheduled to ensure that the Primary Outcome CAPS-5 T4 assessment is within the overall window provided: 105 to 147 days post Visit 3

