10.2.2.1 Cardiovascular and Cerebrovascular Risks and Mitigation

MDMA is known to transiently increase heart rate and blood pressure in a dose-dependent manner that is generally not problematic for physically healthy individuals. These changes should last no more than 8 hours. Participants with PTSD in MAPS-sponsored Phase 2 studies do not appear to differ from healthy individuals in this sympathomimetic, physiological response. Most people do not experience elevations in cardiovascular parameters that exceed those seen after moderate exercise. An examination of safety data drawn from Phase 2 studies of MDMA-assisted psychotherapy detected a dose-dependent increase in systolic blood pressure but not diastolic blood pressure. Characterization of sympathomimetic effects among participants with controlled hypertension is ongoing.

Risks posed by elevated blood pressure will be addressed by excluding people with pre-existing uncontrolled hypertension and monitoring blood pressure and pulse, as described in [Section 4.2 Exclusion Criteria](#). Before and after IMP administration in Experimental Sessions, the therapy team will monitor vital signs. The therapy team will attend to clinical signs and symptoms of potential rare complications of the cardiovascular effects of MDMA, such as stroke or acute myocardial infarction (AMI) during Experimental Sessions. Any symptoms such as chest pain, shortness of breath, neurological deficit or confusion or other potential indicators of end organ effects will prompt additional vital sign measurements, and intervention if appropriate. The therapy team will notify the site physician for evaluation if this occurs.

If any participant has neurological deficits, as assessed by the site physician, whether or not they are associated with hypertensive crisis, they will be monitored, as described above and transported to the hospital if medically indicated. If evaluation at the hospital reveals a nonhemorrhagic stroke, there will be sufficient time to administer recombinant tissue plasminogen within the 3-hour time frame recommended in the American Academy of Neurology/American Heart Association guidelines [107, 108].

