10.2.3.1 Thermoregulatory Risks and Mitigation

MDMA administered in a controlled setting produces only a slight increase in body temperature [110]. Ambient temperature does not enhance or attenuate this slight elevation in humans. In data gathered from sponsor-supported Phase 2 studies, it was found that compared to placebo, a higher percentage of participants receiving MDMA had peak body temperatures greater than 1 degree Celsius (°C) above Baseline. However, there was no strong relationship between dose of MDMA and peak body temperature or between MDMA dose and elevation above threshold of 1°C above Baseline.

Ambient temperature will be kept at a comfortable level during Experimental Sessions. If a participant's temperature rises more than 1°C or the participant states that they feel hot, attempts will be made to decrease body temperature and increase comfort by removing blankets and layers of clothing, decreasing the ambient temperature, and, if necessary, directing a fan toward the

participant. If at any time the temperature rises more than 1.5°C above Baseline despite these efforts, the site physician will be consulted for further evaluation and treatment.

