14.2.2 Safety Analyses

Safety analyses will confirm safety data with summary tables listing exposure to IMP, unsolicited AEs, concomitant medications, suicidal ideation and behavior, and vital signs overall and by group. If a participant has more than one AE mapped to the same PT, that AE will be reported once using the highest severity. AEs that occur on Day 0 (Experimental Session), Day 1, Day 2 after IMP administration will be presented separately. Compare relative incidence of AEs during Experimental Sessions such as clinical signs and symptoms, such as chest pain, shortness of breath, or neurological symptoms or any other signs or symptoms that may be indicative of a medical complication of the IMP.

Frequency and incidence of concomitant medications will be displayed by generic name, sorted by class, and summarized by treatment group, analysis set, and category. Concomitant medications taken on Day 0 (Experimental Session), Day 1, Day 2 after IMP administration will be presented separately. Any psychiatric concomitant medications will be tabulated by period (Preparatory, Treatment Period, Follow-up Period). Frequency and incidence of positive or serious ideation and suicidal behavior will be presented using descriptive statistics of C-SSRS scores in tabular format. Vital signs (heart rate, blood pressure, and body temperature) for Experimental Sessions will be summarized using descriptive statistics in tabular format listing values at pre-IMP administration, prior to the supplemental dose, and at the end of each Experimental Session by treatment group. Additional details are available in the Statistical Analysis Plan.

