3.3 Safety Objectives

The overall safety objective is to assess differences between groups in severity, incidence and frequency of Adverse Events (AEs), Treatment Emergent AEs (TEAEs), AEs of Special Interest (AESIs), and Serious Adverse Events (SAEs), concomitant medication use, suicidal ideation and behavior, and vital signs to support the package insert for MDMA-assisted psychotherapy. The following safety objectives will evaluate the safety of MDMA-assisted psychotherapy compared to identical psychotherapy with inactive placebo:

1. Compare relative incidence of AEs during Experimental Sessions that may be indicative of a medical complication of the Investigational Product (IP) such as clinical signs and

- symptoms of chest pain, shortness of breath, or neurological symptoms or any other signs or symptoms that prompt additional vital sign measurements.
2. Compare relative incidence of AEs by severity.
 3. Compare relative incidence of TEAEs, to determine relationship to the IP based on relative incidence in the MDMA group.
 4. Compare relative incidence of TEAEs by severity reported during an Experimental Session, 1 and 2 days after IP administration.
 5. Compare relative incidence of AESIs, defined as AEs specified in the protocol related to cardiac function and abuse liability.
 6. Compare relative incidence of AEs by severity categorized as leading to discontinuation of IP, resulting in death or hospitalization, and continuing at Termination
 7. Compare relative incidence of SAEs
 8. Compare relative incidence of concomitant medications taken during an Experimental Session, 1 and 2 days after IP administration.
 9. Compare relative incidence of psychiatric concomitant medications taken during the Treatment Period.
 10. Compare relative incidence of positive or serious ideation and suicidal behavior assessed with the Columbia Suicide Severity Rating Scale (C-SSRS) by treatment group.
 11. Compare mean changes in blood pressure, heart rate, and body temperature from pre-IP administration to end of each Experimental Session by treatment group.

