8.0 Analyses

Every effort will be made to ensure complete, accurate and timely data collection and to avoid missing data, to ensure the completeness of the data which can impact the integrity and accuracy of the final study analysis. The statistical analyses will be reported using summary tables, figures, and data listings. All analyses and tabulations will be performed using SAS® Version 9.4 or higher, and S-PLUS. In general, nominal variables will be described in terms of frequencies and percentages and analyzed using chi square analysis. Ordinal and non-normal continuous variables will be described using sample median and range and analyzed by non-parametric statistical tests. Approximately normal variables will be described using sample mean and standard deviations and analyzed by parametric statistical tests. Except for the primary efficacy analysis, all statistical tests will be two-sided and a difference resulting in a p-value of less than or equal to 0.05 will be considered statistically significant. All p-values will be rounded to and displayed in four decimals. If a p-value less than 0.0001 occurs it will be shown in tables as <0.0001. Data not subject to analysis according to this plan will not appear in any tables or graphs, but will be included in the data listings. Selected results may be presented graphically using standard graphical software.

Post-hoc exploratory analyses not identified in this SAP may be performed to further examine the study data. These analyses will be clearly identified as such in the final clinical study report.

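### By-arm vital-sign summaries stop at three scheduled readings per session: no participant-level peak, no as-needed values, and no count above the protocol's own temperature values

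*SAP*

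**What the plan says.** Collection. Protocol Table 5 (section 8.0), footnote C, schedules vital signs in each Experimental Session before dosing, just before the supplemental dose, "and approximately 8 hours after initial dose, and as needed". Protocol 10.2.2.1 adds that symptoms such as chest pain, shortness of breath, neurological deficit or confusion "will prompt additional vital sign measurements, and intervention if appropriate".

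Analysis. SAP 8.8.5 summarises heart rate, blood pressure and temperature descriptively, "listing values at pre-IP, prior to the supplemental dose, and at the end of each Experimental Session by treatment group". Protocol 14.2.2 plans the same: "listing values at pre-IMP administration, prior to the supplemental dose, and at the end of each Experimental Session by treatment group". SAP 8.8.5 then adds one sentence: "Change from Baseline in vital signs will be compared by treatment group with appropriate statistical techniques". Safety objective 11 in SAP 3.3 is narrower: "Compare mean changes in blood pressure, heart rate, and body temperature from pre-IP administration to end of each Experimental Session by treatment group". For everything else, SAP 8.0 states: "Data not subject to analysis according to this plan will not appear in any tables or graphs"; such data go to listings.

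Temperature. Protocol 10.2.3.1 triggers cooling measures at a rise of more than 1 °C and a physician consultation at more than 1.5 °C above Baseline. It describes the Phase 2 experience as a proportion of people: compared with placebo, "a higher percentage of participants receiving MDMA had peak body temperatures greater than 1 degree Celsius" above Baseline.

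**The concern.** Cardiovascular and thermal effects are named risks of MDMA in Protocol section 10.2, and the stated purpose of the safety comparison is to support a package insert. For transient effects of this kind the useful questions are how far each participant's values rose and how many participants rose by a given amount. The planned tables answer neither.

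They give arm-level summaries at three fixed times. The readings taken because something looked wrong appear in no by-arm summary of values. The contrast named in objective 11 ends at the point in the session where a transient rise is least likely to be visible. Phase 2 was described on a participant-level scale for temperature, and the Phase 3 plan has no counterpart to set beside it.

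**Working it through.** There is no plan figure to reproduce. The check sets collection against analysis and then does the clock arithmetic.

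**1. What is collected and what is summarised by arm**

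| Item | Source in the protocol | By-arm summary planned |
|---|---|---|
| Pre-dose reading | Table 5 footnote C; Table 7 (09:55) | Yes |
| Reading before the supplemental dose | Table 5 footnote C; Table 7 (11:30) | Yes |
| End-of-session reading | Table 5 footnote C; Table 7 (17:30) | Yes |
| As-needed readings | Table 5 footnote C | None |
| Symptom-prompted readings | 10.2.2.1 | None for the values; the symptoms are compared as adverse events (SAP 3.3 objective 1, SAP 8.8.2) |
| Largest change per participant | Derivable from the above | None |
| Number above 1 °C and above 1.5 °C | 10.2.3.1; derivable | None |

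So all three scheduled in-session readings are tabulated, one of them after the supplemental dose. There are no planned tables of peak, unscheduled or threshold results.

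**2. When the post-supplemental reading falls**

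- Initial dose at 10:00 and last reading at 17:30 (Table 7): 7.5 h after the initial dose. Table 5 footnote C says about 8 h.
- Supplemental dose: 1.5 to 2 h after the initial dose.
- Shortest interval from supplemental dose to last reading: 7.5 − 2 = 5.5 h.
- Longest interval: 8 − 1.5 = 6.5 h.

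**3. Where peaks would be expected**

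- Protocol 2.2.2 puts peak effects of the initial dose at 1.25 to 2 h. The pre-supplemental reading at 1.5 to 2 h lies inside that window.
- Assumption, not stated in the documents: the supplemental dose has the same lag. Its peak would then fall between 1.5 + 1.25 = 2.75 h and 2 + 2 = 4 h after the initial dose, about 12:45 to 14:00 on the Table 7 clock. No reading is scheduled there; only as-needed readings could be.

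**4. What the objective 11 contrast can show**

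- Protocol 8.3.1 requires at least 8 h counted from 30 minutes before dosing: 09:30 + 8 h = 17:30, the time of the last reading.
- The same section allows the session to be ended when, among other conditions, raised vital signs have returned to pre-dose values.
- A contrast from pre-dose to that point therefore tends towards zero in both arms, whatever happened in between. It also skips the pre-supplemental reading, which is the scheduled reading best placed for the initial dose.

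**5. What Baseline means in SAP 8.8.5**

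- The change sentence names no time point and no method.
- SAP 8.4 takes Baseline resting blood pressure from Screening. Objective 11 uses the pre-dose reading of the session, and Protocol Table 7 also labels that reading Baseline. The reference for blood pressure is therefore open to two readings.

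**The case against.** A reader might infer that nothing measured after the supplemental dose reaches a table. The documents do not support that: the end-of-session reading follows it and is tabulated by arm in both SAP 8.8.5 and Protocol 14.2.2. Nor does the SAP discard a mid-session series. None is scheduled, so the gap between about 2 h and 7.5 h comes mainly from the collection schedule, and new tables can add only sporadic values there.

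A reader might also infer that symptomatic events go unreported. They do not. Objective 1 covers signs and symptoms that prompt extra vital-sign readings, SAP 8.8.2 compares session adverse events by arm, and Protocol 11.1 counts an abnormal sign as an adverse event. What is missing is the measured values, not the events.

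Nor would every excursion vanish into a mean. SAP 1.0 counts minimum, maximum and standard deviation among descriptive statistics, so an extreme at a scheduled time would show. It would show as one value per arm and time point, though, and not as a within-participant rise or a number of participants.

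The change-from-Baseline sentence does not rule out peaks or intermediate times, and SAP 8.0 permits post-hoc analyses. Both are true, but an unspecified comparison and a post-hoc option do not amount to a planned summary.

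The strongest technical objection is selective measurement. The arm measured more often has more chances of a high maximum, so pooling as-needed readings biases the contrast between arms. This stands, and it shapes the fix. It also stands that the temperature values sit under the protocol's low-level risks, and that the documents do not say explicitly that as-needed values are entered in the eCRF.

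**Conclusion.** The point holds as a gap in descriptive safety reporting. In-session vital signs are summarised by arm only at three scheduled times; the one post-supplemental value comes 5.5 to 6.5 h after that dose; and the objective 11 contrast is weakly placed to show a transient rise. Participant-level peak change, as-needed values and counts above 1 °C and 1.5 °C have no planned by-arm table.

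The interval follows from the protocol's own times. The position of a supplemental-dose peak at 2.75 to 4 h rests on the assumed equal lag, and the conclusion does not depend on it. The tendency towards zero rests on the session-ending condition in Protocol 8.3.1. An end-of-session reading taken before values had settled would still show a rise.

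The documents give no standard deviations or excursion rates for vital signs, so the size of any missed effect cannot be computed from them. The primary efficacy inference is unaffected. This is worth correcting before unblinding because it is cheap and because choosing peak summaries afterwards would invite selection.

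**What to change.** In SAP 8.8.5 add, by arm and by Experimental Session, in the Safety Set:

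1. Each participant's maximum post-dose value, and maximum change from the pre-dose reading of the same session, for blood pressure, pulse and temperature.
2. Number and percentage of participants with a temperature rise above 1 °C and above 1.5 °C from that pre-dose reading.

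Show each twice. The scheduled-only version carries the comparison between arms, since both arms are measured at the same times. The version from all recorded readings is labelled descriptive, because as-needed readings are taken selectively.

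Also state that the change-from-Baseline comparison uses the same session's pre-dose reading, and that it covers the pre-supplemental time point as well as end of session.

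The cost is SAP wording and one or two tables. The all-readings version remains subject to selective measurement and depends on as-needed values having been recorded in the database, which should be confirmed. The two temperature values are taken from Protocol 10.2.3.1 and used only for counting; no clinical threshold, dose or measurement schedule changes.

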8.9 Administrative Interim Analysis

An unblinded administrative interim analysis is planned to be performed at a single time point after the first 60% of participants in the *mITT* set have completed the final CAPS-5 follow-up assessment and terminated treatment, including early termination participants who have

completed their final CAPS-5, and 100 participants have been enrolled. The objective of the administrative interim analysis is to conduct a sample size re-estimation. The key secondary endpoint will not be evaluated at the interim analysis. The detailed results of the interim analysis will not be revealed to the site staff, participants, IRs, or sponsor staff/designees except for a single designated sponsor representative from MAPS. The independent DMC statistician will perform the unblinded administrative interim analysis as described in the DMC Charter. In addition, procedures will be developed to ensure the blinding of the participant level data for parties outside of the Independent Statistical Group (ISG).

Sample size re-estimation: Based on the result of calculating conditional power using the estimated effect size from the first 60% of participants in the *mITT* set, the sample size may be increased. The table below shows the range of possible effect sizes that could be observed at the interim analysis and what the guidance from the DMC could be for the adjusted sample size.

Table 6: Observed Effect Sizes and Corresponding Sample Size for 90% Conditional Power Guidance at the Interim Analysis (N=60)

Effect Size	≤ 0.32	0.32	0.34	0.36	0.38	0.40	0.42	0.44
Mean Change	-	5.76	6.12	6.48	6.84	7.2	7.56	7.92
Conditional Power ^[1]	< 50%	52%	60%	67%	74%	80%	85%	89%
Increase in Sample Size to Restore 90% Conditional Power	No increase	240	180	140	110	70	40	10

[1] Conditional Power based on the alternative hypothesis effect size as observed in the first 60 subjects.

For Table 6, the conditional power estimates and the numbers to increase the sample size to restore 90% conditional power were calculated in PASS version 14 using the module for two-sample t-tests, which is based on the conditional power definitions from Jennison and Turnbull [7]. Since the minimum effect size for all possible scenarios where the sample size would be increased achieves greater than 50% conditional power for N=60, the type-I error rate is preserved with this administrative sample size re-estimation method [8]. However, the sponsor has chosen to allocate 2% of the alpha (0.0001) for this unblinded administrative interim analysis to account for any possible downward bias in the variance estimate. At the time of the interim analysis, the independent unblinded statistician will fit the cleaned data on the first 60 participants to the primary analysis model to estimate the parameters. These parameter estimates will be input to the PASS 14 Mixed Model Repeated Measures module to re-estimate the power. If the power is less than 90% and more than 50%, the independent statistician will increase the sample size up to the point where the power reaches 90%. These results will be provided by the unblinded independent statistician to the DMC.

The DMC will review the group-unblinded interim analysis results provided by the independent statistician and will give recommendations to the designated sponsor representative from MAPS. The designated sponsor representative from MAPS will provide written information to the trial organizer delegate of MPBC indicating how many participants, if any, to add to the IWRS but will not provide any information on the corresponding conditional power the additional participants are being added to achieve. Only the re-estimation of sample size will be completed at the interim analysis, this will not be used to drop or add treatment arms or doses, change entry criteria, change randomization ratio or change primary endpoint. The sponsor representative from MAPS will not be part of any trial decisions or administration after the sample size re-estimation has been communicated to MPBC who will continue to be the trial organizer. If the DMC reports a sample size increase to the independent statistician DMC member, they will increase the randomization cap from 100 to the new sample size within the IWRS accordingly. Thereafter, the IWRS will cap randomization at the increased sample size resulting from the interim analysis. If the interim analysis results in a sample size increase, it will not be revealed to the investigators, participants, or sponsor.

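### SAP Table 6 overstates conditional power by 24 to 28 points at its own effect sizes, so its increases miss 90% and its written type I error argument fails in four of seven columns

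*SAP*

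**What the plan says.** SAP section 8.9 (Administrative Interim Analysis) presents Table 6 under the title "Observed Effect Sizes and Corresponding Sample Size for 90% Conditional Power Guidance at the Interim Analysis (N=60"). The footnote defines the quantity: "Conditional Power based on the alternative hypothesis effect size as observed in the first 60 subjects". The method is also stated: the values were "calculated in PASS version 14 using the module for two-sample t-tests", using the Jennison and Turnbull definitions. The table prints:

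- effect size: 0.32, 0.34, 0.36, 0.38, 0.40, 0.42, 0.44
- conditional power: 52, 60, 67, 74, 80, 85, 89%
- increase to restore 90%: 240, 180, 140, 110, 70, 40, 10

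The type I error argument follows directly: "Since the minimum effect size for all possible scenarios where the sample size would be increased achieves greater than 50% conditional power for N=60", the error rate is said to be preserved. The SAP adds that "the sponsor has chosen to allocate 2% of the alpha (0.0001) for this unblinded administrative interim analysis".

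On what is actually done, the text moves between two quantities. The table is introduced as showing "what the guidance from the DMC could be for the adjusted sample size", and Protocol 14.2.3 also speaks of conditional power. The same SAP section then fits the primary model to the interim data: "These parameter estimates will be input to the PASS 14 Mixed Model Repeated Measures module to re-estimate the power". The action rule reads "If the power is less than 90% and more than 50%, the independent statistician will increase the sample size" until power reaches 90%.

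**The concern.** An observed standardised effect of 0.32 on 30 per arm is an interim Z of only about 1.24. A conditional power of 52% at 100 participants looks too high for that. The re-estimation is the trial's only adaptive decision, it uses unblinded data, and the final analysis uses the conventional test at 0.0499. The SAP therefore depends on its claim that every increase happens above 50% conditional power.

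If the printed values are wrong, three things follow. The written ground for type I error control fails. A decision guided by the table would add participants where the SAP's own floor says not to, and too few or none where it says to add. And the stated 90% would not be reached. Separately, if the table and the action rule use different quantities, they can give different sample sizes from the same interim data.

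**Working it through.** **Inputs.**

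- Interim: 60 participants (Table 6 title and footnote), 30 per arm under 1:1 allocation (Protocol 9.3).
- Planned final size: 100, or 50 per arm (SAP 8.9, randomization cap; SAP 8.2, N=100 in the mITT set).
- Test: two-sided alpha 0.0499 (SAP 8.7.1), z = 1.9608.
- Drift: the observed effect size θ (Table 6 footnote).
- Increases are read as total participants.

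**Formula.** With information I = (n per arm)/2, I1 = 15 and I2 = 25, the interim statistic is Z1 = θ√I1, and

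CP = Φ[(Z1√I1 − z√I2 + θ(I2 − I1)) / √(I2 − I1)].

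At θ = 0.32 this is (4.80 − 9.80 + 3.20)/√10 = −0.571, so CP = 28.4%. After the tabled +240, N = 340 and I2 = 85: (4.80 − 1.9608 × 9.220 + 0.32 × 70)/8.367 = 1.090, so CP = 86.2%.

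| Effect size | CP printed | CP recomputed | Increase printed | CP after that increase | Increase needed for 90% |
|---|---|---|---|---|---|
| 0.32 | 52% | 28.4% | 240 | 86.2% | 285 |
| 0.34 | 60% | 34.0% | 180 | 84.1% | 237 |
| 0.36 | 67% | 40.0% | 140 | 83.0% | 198 |
| 0.38 | 74% | 46.2% | 110 | 82.6% | 164 |
| 0.40 | 80% | 52.5% | 70 | 78.9% | 135 |
| 0.42 | 85% | 58.7% | 40 | 75.6% | 110 |
| 0.44 | 89% | 64.7% | 10 | 69.6% | 88 |

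Conditional power passes 50% at an effect size of 0.392 and 90% at 0.554; Table 6 puts these at about 0.32 and 0.44. At 0.50 it is 80% and about 36 more participants are needed, yet the table stops at 0.44.

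**Sensitivity.** A t critical value on 98 df gives 27.1% to 63.3%. A final size of 47 per arm gives 24.8% to 61.3%. Simulating the pooled t-test with the interim effect fixed (40,000 runs) gives 28.4%, 51.9% and 64.1% at 0.32, 0.40 and 0.44. A one-sided 0.0499 test comes closer but is still off by up to 9 points, and it is not the stated test.

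**Where the printed figures may come from.** No PASS inputs are shown, so this is inference.

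- Interim Z too large by √2 (Z1 = θ√30): CP is 52.3, 60.1, 67.5, 74.2, 80.2, 85.2, 89.3%, and the tabled increases then give 89.9% to 90.8%. This matches both rows at 60 of 100.
- The Mean Change row divided by the section 7.0 planning SD on the CAPS-5 scale, √(335 + 280) × 20/34 = 14.59: CP is 50.8% to 88.3%, but only +142 down to +7 would be needed. It also contradicts the printed effect sizes, because Mean Change divided by effect size is 18.0 in every column.
- About 46 of 78 per arm reproduces the conditional powers, with 90.5% to 92.0% after the tabled increases, but that design appears in neither document.

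**Type I error.** The conditional error under the null is Φ[(Z1√I1 − z√I2)/√(I2 − I1)]. At N = 100, then after the tabled increase, it is 0.0568/0.0563, 0.0684/0.0637, 0.0819/0.0723, 0.0972/0.0824, 0.1145/0.0979, 0.1339/0.1180 and 0.1555/0.1488. It falls in every column. The margin is thinnest at 0.32, where the break-even effect size for N = 340 is 0.318. Integrating over Z1 gives an overall two-sided error of 0.0483 to 0.0493, depending on whether the increases are read stepwise or interpolated, and in one or both directions.

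**Which rule.** If the power in the action rule is unconditional, a two-sample approximation (not a mixed-model run) is Φ(θ√25 − z). At 0.32 this is Φ(1.60 − 1.96) = 36%, so no increase, against +240 in Table 6. At 0.40 it is Φ(2.00 − 1.96) = 52%, and 90% needs about +164, against +70.

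**Alpha percentage.** 0.0001/0.05 = 0.002, which is 0.2%, not 2%.

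**The case against.** The strongest reply is that nothing inferential is damaged. The SAP concludes that type I error is preserved, and for Table 6 as printed that is true, because conditional error falls in every column. The final test, its alpha and the estimate are untouched. Table 6 is offered only as possible guidance; the action is described through the mixed-model module, and the DMC Charter, which is not among the documents, may settle the matter. The √2 explanation is one of more than one that fit the conditional-power row.

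Much of this stands. There is no inflation, no passage shows that Table 6 drove the decision, and the cause is unconfirmed. The repeated 0.32 boundary is minor and may be a text-extraction artefact.

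It does not rescue the table or the argument. A correct conclusion reached from a false premise is still an invalid justification in a confirmatory plan, and the SAP gives no other: the 0.0001 is assigned to possible bias in the variance estimate. That two quantities could govern the decision is itself a defect. None of the alternative fits corresponds to 60 of 100 with the printed effect sizes and a correctly scaled interim Z.

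**Conclusion.** The concern holds. At the documented design, Table 6 overstates conditional power by 24 to 28 points in every column. Its increases reach 70% to 86%, not 90%, and the above-50% premise is false at 0.32, 0.34, 0.36 and 0.38. If the table guided the decision, it would add 110 to 240 participants below the SAP's own floor and too few or none where conditional power lies between 50% and 90%.

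This rests on 30 and 50 per arm, the two-sided 0.0499 test, the current-trend drift named in the footnote, and increases read as total participants. The count of four columns depends on the two-sided test: at one-sided 0.0499 only 0.32 would fall below 50%.

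The defect is a false justification, wrong stated powers, an unclear rule and a wrong percentage. It is not an inflated error rate. It must be fixed, because the written basis for error control in the trial's only adaptive step has to be true.

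**What to change.** - Recompute Table 6 with interim Z = θ√(n1·n2/(n1 + n2)), where n1 and n2 are the interim numbers in the two arms. Restate the conditional powers, the increases for 90%, and the effect sizes at which conditional power passes 50% and 90%. State the PASS inputs and the source of the SD of 18 implied by the Mean Change row.
- Replace the type I error argument with one that holds for the rule actually used: the calculated overall error rate, a column-by-column conditional-error check, or a combination test.
- State which single quantity governed the decision, conditional power or mixed-model power.
- Correct 2% to 0.2% and give 0.32 one place in the table.
- SAP 8.7.2 puts the interim data cutoff at 11 March 2020, so the decision rule should not be changed retrospectively. The independent statistician should document which rule and calculation were applied and what the corrected calculation gives. That note should stay with the DMC and the independent statistical group until database lock, in keeping with the confidentiality terms of SAP 8.9.

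The cost is one re-run of the calculation, some SAP wording and the note. The stated conditional powers will look less favourable, and the note may show that the interim decision differed from what the corrected calculation gives.
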